#### **4.3.7 Intra-Patient Dose Escalation with Cabiralizumab and Nivolumab**

Intra-patient dose escalation is not allowed for nivolumab or cabiralizumab.

#### **4.3.8 Treatment beyond Disease Progression with Cabiralizumab and Nivolumab**

Accumulating evidence indicates a minority of patients treated with immunotherapy may derive clinical benefit despite initial evidence of progressive disease [REDACTED]

Patients treated with cabiralizumab and nivolumab combination therapy will be permitted to continue cabiralizumab and nivolumab treatment beyond initial RECIST v1.1 defined progressive disease, assessed by the Investigator, as long as the following criteria are met:

- Patients who will be treated beyond disease progression must review and sign an ICF before continuing on study drug
- The patient demonstrates investigator-assessed clinical benefit, and do not have rapid disease progression
- Tolerance of study drugs
- Stable performance status
- Treatment beyond progression will not delay an imminent intervention to prevent serious complications of disease progression (e.g., CNS metastases)

A radiographic assessment/scan should be performed approximately 8 weeks ( $\pm 7$  days) after initial Investigator-assessed progression to determine whether there has been a decrease in the tumor size or continued progressive disease. The assessment of clinical benefit should be balanced by clinical judgment as to whether the patient is clinically deteriorating and unlikely to receive any benefit from continued treatment with cabiralizumab and nivolumab.

If the Investigator feels that any patient receiving cabiralizumab and nivolumab will obtain clinical benefit by continuing treatment, the patient may remain on the trial and continue to receive monitoring according to the time and event schedules per protocol.

For the patients who continue cabiralizumab and nivolumab study therapy beyond progression, further progression is defined as an additional 10% increase in tumor burden from time of initial progression. This includes an increase in the sum of diameters of all target lesions and/or the diameters of new measurable lesions compared to the time of initial progression. cabiralizumab and nivolumab treatment should be discontinued permanently upon documentation of further progression.

#### 4.3.9 Dose Modification Algorithms for Immuno-Oncology Agents

Immuno-oncology agents are associated with AEs that can differ in severity and duration compared to AEs caused by other therapeutic classes. Cabiralizumab and nivolumab are considered immuno-oncology agents in this protocol. Early recognition and management of AEs associated with immuno-oncology agents may mitigate severe toxicity. Management algorithms have been developed to assist Investigators in assessing and managing the following classes of AEs:

- Gastrointestinal
- Renal
- Pulmonary
- Hepatic
- Endocrinopathy
- Skin
- Neurological
- Infusion reaction
- Periorbital edema
- Uveitis
- Laboratory abnormalities

#### 4.3.10 Treatment of Cabiralizumab and Nivolumab-Related Infusion Reactions

Cabiralizumab and nivolumab may induce infusion or hypersensitivity reactions. If such a reaction were to occur, it may manifest with fever, chills, rigors, headache, rash, pruritus, arthralgia, hypo- or hypertension, bronchospasm, or other symptoms.

Infusion reactions should be graded according to CTCAE v4.03 guidelines. Any Grade 3 or Grade 4 infusion reaction should be reported within 24 hours to the Sponsor's Medical Monitor or designee, and reported as an SAE if it meets the criteria.

The nivolumab 30-minute infusion will be administered first, with a 30- to 60-minute rest, followed by the cabiralizumab 30-minute infusion. It may be unclear if an infusion reaction is due to cabiralizumab, nivolumab, or to both study drugs. Therefore, one set of treatment recommendations (based on the most conservative treatments for infusion reactions due to either study drug) is provided below and may be modified based on clinical judgment, local treatment standards and guidelines, and/or specific symptoms, as appropriate:

**For Grade 1 symptoms:** Mild reaction (e.g., localized cutaneous reactions including mild pruritus, flushing, rash), requires infusion rate to be decreased; intervention may be indicated.

- Decrease the rate of the study drug infusion until recovery from symptoms.
- Remain at bedside and monitor the patient's vital signs until resolution of symptoms. Diphenhydramine 50 mg may be administered at the discretion of the treating physician.
- When symptoms resolve, restart the infusion at the original infusion rate.
- If a patient has an infusion reaction with nivolumab, cabiralizumab can be given (without prophylactic medications) if the infusion reaction resolves within 3 hours. For scheduling purposes, cabiralizumab infusion may be given the next day. Prophylactic pre-infusion medications should be given prior to all subsequent nivolumab infusions.
- If a patient has an infusion reaction with cabiralizumab, prophylactic pre-infusion medications should be given prior to all subsequent cabiralizumab and nivolumab infusions.
- The following prophylactic pre-infusion medications are recommended prior to future infusions of cabiralizumab and nivolumab: diphenhydramine 50 mg (or equivalent) and/or paracetamol (acetaminophen) 325 to 1000 mg at least 30 minutes before additional study drug administrations.

**For Grade 2 symptoms:** Moderate reaction (i.e., any symptom not listed above [mild symptoms] or below [severe symptoms] such as generalized pruritus, flushing, rash, dyspnea, hypotension with systolic blood pressure >80 mmHg), requires infusion interruption but responds promptly to symptomatic treatment (e.g., antihistamines, nonsteroidal anti-inflammatory drugs, narcotics, corticosteroids, IV fluids); prophylactic pre-infusion medications indicated for  $\leq 24$  hours.

- Interrupt the study drug infusion.
- Begin an IV infusion of normal saline, and treat the patient with diphenhydramine 50 mg IV (or equivalent) and/or paracetamol (acetaminophen) 325 to 1000 mg.
- Remain at bedside and monitor the patient's vital signs until resolution of symptoms. Corticosteroid therapy may be administered at the discretion of the treating physician.
- When symptoms resolve, restart the infusion at 50% of the original infusion rate; if no further complications ensue after 30 minutes, the rate may be increased to 100% of the original infusion rate.
- Monitor the patient closely. If symptoms recur, immediately discontinue the infusion; no further study drug will be administered at that visit. Administer diphenhydramine 50 mg IV, and remain at bedside and monitor the patient until resolution of symptoms.
- If a patient has an infusion reaction with nivolumab infusion, cabiralizumab infusion can be given (without prophylactic medications) if the infusion reaction resolves within 3 hours. For scheduling purposes, the cabiralizumab infusion may be given the next day.

Prophylactic pre-infusion medications should be given prior to all subsequent nivolumab infusions.

- If a patient has an infusion reaction with cabiralizumab, prophylactic pre-infusion medications should be given prior to all subsequent cabiralizumab and nivolumab infusions.
- The following prophylactic pre-infusion medications are recommended prior to future infusions of cabiralizumab and nivolumab: diphenhydramine 50 mg (or equivalent) and/or paracetamol (acetaminophen) 325 to 1000 mg should be administered at least 30 minutes before additional study drug administrations. If necessary, corticosteroids (up to 25 mg of SoluCortef or equivalent) may be used.
- The amount of study drug infused must be recorded.

**For Grade 3 or Grade 4 symptoms:** Severe reaction such as bronchospasm, generalized urticaria, systolic blood pressure <80 mmHg, or angioedema; Grade 3 symptoms including prolonged symptoms, which require 6 or more hours to respond to symptomatic medication and/or discontinuation of infusion; recurrence of symptoms following initial improvement; hospitalization indicated for other clinical sequelae, such as renal impairment, pulmonary infiltrates; Grade 4: life-threatening; pressor or ventilation support indicated.

- Immediately discontinue the study drug infusion. No further study drug will be administered. The amount of study drug infused must be recorded on the CRF.
- Begin an IV infusion of normal saline, and treat the patient as follows: Recommend bronchodilators, epinephrine 0.2 to 1.0 mg of a 1:1,000 solution for subcutaneous administration or 0.1 to 0.25 mg of a 1:10,000 solution injected slowly for IV administration, and/or diphenhydramine 50 mg IV with methylprednisolone 100 mg IV (or equivalent), as needed.
- Remain at bedside and monitor the patient's vital signs until recovery from symptoms.
- The patient should be monitored until the Investigator is comfortable that the symptoms will not recur.
- Investigators should follow their institutional guidelines for the treatment of anaphylaxis.

In the case of late-occurring hypersensitivity symptoms (e.g., appearance of a localized or generalized pruritus within 1 week after treatment), symptomatic treatment may be given (e.g., oral antihistamine, or corticosteroids).

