#### 4.3.3 Criteria to Resume Treatment with Cabiralizumab and Nivolumab

Patients may resume treatment with cabiralizumab and/or nivolumab when the drug-related AE resolves [REDACTED]

[REDACTED] The Sponsor's Medical Monitor or designee can be contacted at any time if further clarification is needed.

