#### 4.3.5 Dose Discontinuation Criteria for Cabiralizumab and Nivolumab

Discontinuation rules may be different for monotherapy and combination therapy and not all rules will apply to both arms of the study. [REDACTED]

Treatment of cabiralizumab in monotherapy or cabiralizumab in combination with nivolumab should be discontinued in the following cases unless otherwise specified:

- Any Grade 3 or higher uveitis *or* any Grade 2 drug-related uveitis, eye pain, or blurred vision that does not respond to topical therapy and does not improve to Grade 1 within the second re-treatment period *or* that requires systemic treatment
- Any Grade 3 or higher infusion-related reactions and hypersensitivity requiring discontinuation. Any re-initiation of therapy in this circumstance would require consultation with the Sponsor's Medical Monitor or designee.
- Any Grade 3 non-skin, drug-related AE lasting >7 days, including drug-related uveitis, pneumonitis, hypoxia, bronchospasm, and endocrinopathies with the following exceptions:
  - Grade 3 drug-related endocrinopathies adequately controlled with only physiologic hormone replacement do not require discontinuation
  - Grade 3 drug-related laboratory abnormalities do not require treatment

discontinuation except:

- Grade 3 drug-related thrombocytopenia >7 days or associated with Grade  $\geq 2$  bleeding requires discontinuation
- Any drug-related liver function test (LFT) abnormality that meets any one of the following criteria requires discontinuation:
  - ALT or AST >3x ULN **and** total bilirubin >2x ULN **or** INR > 1.5 xULN (in the absence of anticoagulation).
  - [REDACTED]
  - ALT or AST > 20x ULN (with or without concurrent liver metastases)
  - Total bilirubin >3x ULN (>5x ULN with concurrent liver metastases)
- Any Grade 4 drug-related AE or laboratory abnormality, except for the following events which do not require discontinuation:
  - Grade 4 neutropenia <7 days
  - Grade 4 lymphopenia or leukopenia <7 days
  - Isolated Grade 4 amylase or lipase abnormalities that are not associated with symptoms or clinical manifestations of pancreatitis. The Sponsor’s Medical Monitor or designee should be consulted for Grade 4 amylase or lipase abnormalities.
  - Isolated Grade 4 electrolyte imbalances/abnormalities that are not associated with clinical sequelae and are corrected with supplementation/appropriate management within 72 hours of their onset

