### 7.3.2 Phase 1b Endpoints

#### 7.3.2.1 Primary

- **Efficacy**
  - ORR will be defined as the total number of patients with confirmed responses of either CR or PR divided by the total number of patients who are evaluable for a response per RECIST v1.1 by investigator assessment

- Safety
  - The incidence of AEs, SAEs, clinical laboratory abnormalities, and ECG abnormalities
  - The incidence of treatment discontinuations, modifications, and interruptions due to adverse events
  - Grade 3 and Grade 4 AEs and clinical laboratory abnormalities

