## 7.6 Safety

Unless otherwise specified, all analyses will be performed using the safety population.

Adverse events (AEs) will be coded according to the most current version of MedDRA and be graded using the NCI Common Terminology Criteria for Adverse Events (CTCAE) version *4.03*. Treatment-related AEs are those events with relationship to study treatment "Related" as recorded on the CRF. If the relationship to study treatment is missing, the AE will be considered as treatment related.

Listing of adverse events will include all enrolled subjects, as SAEs and deaths are collected pretreatment. Summaries of adverse events will be for treatment-emergent AE (TEAE) that is defined as adverse event starts or severity becomes worse after the first dose and within 100 days of last study therapy. AEs and treatment-related AEs will be tabulated by descending frequency of SOC and descending frequency of PT within each SOC, unless specified otherwise.

When reporting adverse events by CTC grade, summary tables will be provided based on the event with worst CTC grade (independent of relationship to study medication). Subjects will only be counted (1) once at the preferred term (PT) level, (2) once at the system organ class (SOC) level, and (3) once in the 'Total subject' row at their worst CTC grade, regardless of SOC or PT.

The analysis of laboratory results will be based on safety population with data. Laboratory results will be categorized according to NCI CTCAE (version *4.03*) grade. Baseline is defined as the last non-missing measurement prior to the first dosing date and time.

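### Protocol 4.3.10 gives a recurring infusion reaction the Grade 2 action, a stop for that visit only, although the same section lists such a recurrence as Grade 3

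*Protocol*

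**What the plan says.** Protocol 4.3.10 gives one set of infusion-reaction recommendations for both study drugs, arranged by grade. Its opening paragraphs require grading by CTCAE v4.03, allow the recommendations to be modified by clinical judgment, and add: "Any Grade 3 or Grade 4 infusion reaction should be reported within 24 hours to the" Sponsor's Medical Monitor or designee.

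Under Grade 2, the infusion is interrupted, restarted at half the original rate once symptoms resolve, and may return to full rate after 30 minutes without complications. The next instruction is: "If symptoms recur, immediately discontinue the infusion; no further study drug will be administered at that visit". Later Grade 2 bullets recommend premedication before future infusions, so they assume that dosing continues. The Grade 2 definition covers only symptoms that are in neither the mild nor the severe list.

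Under Grade 3 or 4, the description of Grade 3 includes "recurrence of symptoms following initial improvement", and the first instruction is: "Immediately discontinue the study drug infusion. No further study drug will be administered". It carries no visit limit.

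Protocol 4.3.5 lists among its discontinuation criteria: "Any Grade 3 or higher infusion-related reactions and hypersensitivity requiring discontinuation. Any re-initiation of therapy in this circumstance would require consultation" with the Medical Monitor or designee. Protocol 4.3.3 begins "Patients may resume treatment with cabiralizumab and/or nivolumab when the drug-related AE resolves" and is then redacted.

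**The concern.** One sequence of events (symptoms resolve, the infusion restarts, symptoms return) is covered by two adjacent paragraphs. The bullet written for exactly that sequence sits under Grade 2 and limits the stop to one visit. It does not say that the grade has changed, and it refers neither to the Grade 3 or 4 paragraph nor to 4.3.5. Staff who go to the bullet that matches what they see will find the weaker action.

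Several other rules depend on the grade. If the event is handled and recorded as Grade 2, these may not be applied:

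- the 24-hour report to the Medical Monitor (4.3.10);
- consultation before re-initiation (4.3.5);
- the change from 30- to 60-minute nivolumab infusions for all current and later patients after any Grade 3 or higher reaction at the 30-minute rate (4.3.1.1);
- DLT assessment in Phase 1a escalation, where Grade 3 is the threshold (3.1.2.1.1).

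The Phase 1b primary safety endpoint "Grade 3 and Grade 4 AEs and clinical laboratory abnormalities" (Protocol 7.3.2.1) also depends on the grade, because under SAP 7.6 "summary tables will be provided based on the event with worst CTC grade".

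**Working it through.** The plan states no figure on this point, so the main check is a comparison of the texts.

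| Step | Grade 2 recurrence bullet | Grade 3 or 4 paragraph, with 4.3.5 |
|---|---|---|
| Infusion in progress | Stopped at once | Stopped at once |
| Acute treatment named | Diphenhydramine 50 mg IV | Bronchodilators, epinephrine, diphenhydramine with methylprednisolone, as needed |
| Monitoring | Until symptoms resolve | Until recovery, and until the investigator is comfortable that symptoms will not return |
| Report within 24 hours | Not mentioned | Required |
| Further study drug | Barred for that visit | Barred without a visit limit; re-initiation after Medical Monitor consultation |

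**Which grade applies?** The Grade 2 definition leaves out anything in the severe list. That list names recurrence after improvement as Grade 3. A reaction that returns after the restart has, by the protocol's own description, left Grade 2. So the text does settle the grade, and the bullet gives an action that does not fit it.

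**How do the paths differ for dosing?** In Phase 1b the next dose is due 14 days later, and no sooner than 12. On the visible text, the Grade 2 path reaches that dose with premedication. The Grade 3 path reaches it only after a report and a Medical Monitor contact.

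**What reaches the DLT count?** Section 3.1.2.1.1 exempts a Grade 3 infusion-related AE that resolves within 6 hours of onset, but counts any recurrence of a Grade 3 infusion-related AE. The first episode here was Grade 2, so on a plain reading the returning reaction is the first Grade 3 event. It is a DLT if it is drug-related, falls within the DLT window and does not resolve within 6 hours. Where it does count, one event matters: with 0 of 3 evaluable patients the dose escalates, and with 1 of 3 the cohort takes 3 more patients (3.1.2.1).

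**What reaches the 60-minute rule?** It is triggered by a Grade 3 or higher reaction at the 30-minute nivolumab rate. The protocol does not say whether a recurrence during the half-rate restart counts. A recurrence after return to full rate fits the rule more directly.

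**Size in the Phase 1b tables.** Cohorts have about 30 patients, and Phase 1b about 210 in all. Let k be the number of patients recorded as Grade 2 instead of Grade 3. The change in incidence is at most k/n.

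- k = 1: 1/30 = 3.3 percentage points; 1/210 = 0.5 points.
- k = 3: 3/30 = 10.0 points; 3/210 = 1.4 points.

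The documents give no recurrence rate, so k from 0 to 3 is an assumption that only shows scale. In the total-subject row of SAP 7.6 the change is zero for a patient who already has another event of Grade 3 or higher. The preferred-term row still changes unless that other event has the same term.

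**What does not move.** Infusion interruptions (SAP 7.4.2) are counted without regard to grade. SAP 7.6.3 counts only permanent discontinuation, so a patient who is re-dosed is not counted on either path. ORR is not involved.

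**The case against.** The strongest reply is that the documents already give the answer. CTCAE grading is mandatory, the Grade 2 definition excludes the severe list, and the Grade 3 entry is in the next paragraph. The grade on the case report form comes from CTCAE, not from the management bullet a nurse followed. On this view only a pointer is missing. Much of this stands: the grade can be worked out, and misgrading needs a site to overlook a stated rule. But the bullet is more than a gap. It gives a positive instruction for this exact event, and that instruction belongs to the lower grade.

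The second reply concerns text that cannot be seen. Sections 4.3.1, 4.3.2, 4.3.3 and the introduction to 4.3.5 contain redactions, and the infusion-reaction algorithm named in 4.3.9 is not visible. Any of these could hold the link or a re-dosing rule. That stands as a limit on the consequences. It does not change the wording of the bullet, which is fully visible.

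Three stronger readings are tempting and are not supported:

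- A reader might infer that the bullet permits dosing that the Grade 3 text bans for good. It does not: 4.3.5 allows re-initiation after consultation, its qualifier about reactions that require discontinuation may narrow it further, and 4.3.10 yields to clinical judgment.
- A reader might infer that cabiralizumab can follow the next day after a recurrent nivolumab reaction. The Grade 2 text offers next-day dosing for a nivolumab reaction, with same-day dosing tied to resolution within 3 hours. It does not say that this option survives a recurrence.
- A reader might infer a material bias in the Grade 3 or 4 rates. Without a recurrence rate, no such size can be claimed.

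**Conclusion.** The point holds as an inconsistency in a safety instruction. By the protocol's own description the event is Grade 3, yet the bullet that addresses it gives the Grade 2 action. The possible consequences are a missed 24-hour report, re-dosing without Medical Monitor consultation, a missed trigger for 60-minute nivolumab infusions and, in Phase 1a escalation, a missed DLT assessment. In the Phase 1b safety tables each affected patient counts for at most 3.3 points in 30 or 0.5 in 210.

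This rests on three assumptions: that some sites would act on the bullet without reading on, that the redacted text does not already close the gap, and, for the DLT and 60-minute rules, that the event meets their further conditions. No frequency is claimed. The correction is worth making because it is cheap and about 50 centers work from this text.

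**What to change.** Replace the recurrence instruction under Grade 2 in 4.3.10 with wording such as:

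*If symptoms recur after the restart, stop the infusion at once. The reaction is then Grade 3 (CTCAE v4.03); manage and report it under the Grade 3 or 4 instructions below. Any re-initiation of the study drug or drugs follows Section 4.3.5, including Medical Monitor consultation and that section's provision for continuing the non-offending drug.*

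The last clause matters. Section 4.3.5 lets the other drug continue when causality is confirmed and its listed conditions are met, and a blanket consultation rule for both drugs would conflict with that. Keep the Grade 2 premedication advice for any patient who is restarted.

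The change is a short replacement in an amendment. It brings a few more events graded 3 and a Medical Monitor contact before these patients are re-dosed. It may also bring the 60-minute nivolumab rule or a DLT review into play. Both already follow from the protocol's own Grade 3 description, so the amendment applies existing rules and adds none.

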#### **4.4 Method of Assigning Patient Identification**

Patients must be able to provide written informed consent and meet all eligibility criteria. No waivers of inclusion or exclusion criteria will be granted by Sponsor or its designee for any patient enrolled in the study. Before enrolling a patient, all eligibility criteria must be satisfied.

Patients who qualify for Phase 1a dose escalation of the study will be enrolled as follows:

- The 2 mg/kg cabiralizumab monotherapy cohort was enrolled first, followed by enrollment to the 1mg/kg cabiralizumab /nivolumab combination cohort. Patients in these cohorts will be treated for a total of two 14-day treatment cycles within the DLT period.
- Enrollment into the 4 mg/kg cabiralizumab monotherapy cohort will proceed once the DLT period is cleared in preceding monotherapy cohorts.
- Dose escalation into increasing dose levels of cabiralizumab in combination with nivolumab may proceed until DLTs are observed either in the cabiralizumab monotherapy or the cabiralizumab in combination with nivolumab cohorts after discussion and agreement by the Cohort Review Committee.

In 3-week dosing regimen Cohort (1aD), approximately 10 patients will be enrolled into the 4 mg/kg cabiralizumab in combination with nivolumab cohort. These patients will receive study treatment every three weeks.

The Phase 1a exploration consists of six cohorts of approximately 10 patients each. These cohorts are further evaluating the safety, PK, and PD of cabiralizumab as monotherapy and in combination with nivolumab.

In Phase 1b, approximately 30 patients will be enrolled per cohort. Enrollment will be open for all cohorts in parallel and will continue until the enrollment target is reached. Once a cohort is filled, further enrollment will be restricted to the cohort(s) that have not been filled. A total of approximately 210 patients will be enrolled in the Phase 1b arm of the study.

The Investigator may repeat qualifying lab tests and vitals/ECGs prior to enrollment if a non-qualifying finding is considered an error or an acute finding is likely to meet eligibility criteria upon repeat testing.

